Eligibility screening: Regardless of where the potential participant learned about the study, all potential participants will be screened for the study by completing a survey hosted by REDCap that connected the potential participant to a consulting therapist (a Talkspace staff member who completes intake for all Talkspace services) in Talkspace's HIPAA compliant, encrypted text platform. All patients seeking services from Talk Space complete a PHQ-9 during their initial screening. If a patient meets eligibility criteria for the study, the consulting therapist will ask if they wish to learn more about the study. If so, the consulting therapist proceeds with the consent procedures. If the potential participant does not meet criteria for the study, the consulting therapist will discuss alternate treatment options with the potential participant. The PHQ-9 scores collected on Talkspace will not be retained as part of study data. Phase 2 participants will provide information needed to assess eligibility including date of birth, location, PHQ-9, phone number, email address, and primary language prior to enrollment. This information is retained as part of study data.

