4.4 Inclusion and Exclusion Criteria

Inclusion criteria:

Phase 1: 18 years old and older, English and/or Spanish speaking, living in the US, PHQ-9 score ≥ 10 , and received a diagnosis of depression from a Talkspace intake clinician.

Phase 2: 18 years old and older, English and/or Spanish speaking, living in the US in a state where a participating licensed Talkspace clinician is available, PHQ-9 score ≥ 10 .

- Prolific recruitment survey: Prolific users who are 18 years old and older, English speaking, living in the US in a state where a participating licensed Talkspace clinician is available.

Unavailable therapist: Potential participants who are eligible at an initial baseline but unable to enroll in the study due to lack of therapist availability will be contacted by Talkspace via email to let them know. In that email, they will be offered immediate care at Talkspace and will be told that they will be contacted when a study therapist is available, unless they opt out of further communication. Once a study therapist is available in their state, any waiting potential participants will either be randomized or, if it has been more than 30 days since their initial eligibility baseline, will be sent a link to complete a new baseline. All eligibility criteria should still be met at the new baseline in order for the participant to be randomized. However, participants with PHQ-9 scores between 5 and 10 may be randomized if they remain interested in participating in the study. No one with a PHQ-9 score < 5 will be randomized. The study team will remove recruitment materials from states with no therapist capacity, so these situations should be limited to individuals that enter the enrollment pipeline while space is available but do not complete the enrollment activities prior to a therapist's caseload filling.

Exclusion criteria:

Phase 1: Under 18 years of age, does not speak English or Spanish, and does not meet criteria for a depressive disorder. Individuals with active suicidal ideation or with a primary diagnosis of psychosis will be excluded and referred to appropriate care.

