5.2 Study Assessments

Baseline Assessments:

- Demographics
- MDE Screener

- 9-item Patient Health Questionnaire (PHQ-9)
- 8-item Neuro-Quality of Life v1.0 (Neuro-QOL) Ability to Participate in Social Roles and Activities short form (Phase 2 only)
- 7-item Generalized Anxiety Scale (GAD-7)
- NIAAA Alcohol Screening Test
- IMPACT Assessment of Mania and Psychosis
- Self-reported health and health concerns
- Use of other apps and mental health treatment
- Participant Top Issue & Follow-Up Question (Phase 2 only)
- Perceived Stress Scale (Phase 2 only)
- Past Mental Health Treatment Experiences (Phase 2 only)
- Random Assignment Level 1 Reaction Questions (Phase 2 only)

Daily Assessments: Participants will be asked to answer brief, daily questions intended to capture information on daily fluctuations in mood, social and physical activity, and sleep.

Weekly Assessments:

- 9-item Patient Health Questionnaire (PHQ-9)
- 8-item Neuro-Quality of Life v1.0 (Neuro-QOL) Ability to Participate in Social Roles and Activities short form (Phase 2 only)
- 7-item Generalized Anxiety Scale (GAD-7)
- Patient Global Improvement Scale
- Major Life Event & Impact on Treatment (Phase 2 only)
- Participant Top Issue & Follow-Up Question (Phase 2 only)
- Therapist Contact Weekly Question

Week 1: Treatment Rationale Scale

Weeks 2 and 7: Credibility Expectancy Scale (Patient's Version) (Phase 2 only)

Weeks 4, 8, and 12:

- Major Life Changes
- Satisfaction with Care
- Perceived Stress scale (Phase 2 only)

Weeks 4 and 10:

- Experience of Care and Health Outcomes Survey (ECHO)
- Working Alliance Inventory-Short Revised (WAI-SR)

Week 12: Exit survey.

Early exit survey: Early drop out participants will be asked to complete a 1-question early exit survey (Phase 2 only).

Talkspace data: Talkspace meta-data (number of text interactions, time texting, time between texts, number of sessions) and content data including transcripts are collected on the Talkspace platform. All identifiable information (e.g., names, usernames, links) are scrubbed from the transcripts by an automated process internal to Talkspace prior to transfer to UW. Additionally, we will collect data on treatment intensity from Talkspace's electronic record of patient contact, which consists of time spent in treatment, number of sessions/messages over 12 weeks, and treatment attendance.

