1. Test effectiveness of unlimited daily, message-based psychotherapy (MBP) for depression, compared to weekly traditionally delivered, videoconferencing-based psychotherapy (VBP). Level 1 conditions: unlimited MBP and weekly VBP.
2. Develop an evidence-based treatment sequence for those who do not respond to either MBP or VBP. Level 2 conditions for participants who do not respond to treatment: MBP+VBP_{weekly} (switch from MBP to weekly VBP with MBP), MBP+VBP_{monthly} (switch from MBP to monthly VBP with MBP), VBP_{weekly}+MBP (switch from VBP to weekly VBP with MBP), and VBP_{monthly}+MBP (switch from VBP to monthly VBP with MBP).

Hypothesis 1: Compared to those randomized to weekly video care at baseline, patients randomized to message-based care will have greater improvements in depression (1a) and social functioning (1b), be more likely to show a treatment response (1c), and be more likely to experience remission (1d) at 5 and 12 weeks of care. Hypothesis 2: For those who fail to respond to treatment from baseline to 5 weeks, those re-randomized to receive (or retain) weekly video care will have greater improvements in depression and be more likely to show a response to treatment than those randomized to monthly video care. Hypothesis 3 (moderator): Baseline anxiety will moderate improvement in depression such that those with greater anxiety will have better response to message-based care at 5 and 12 weeks than to video-based care. Exploratory Aims: Exploratory evaluation of differences among groups in treatment engagement by week 5, ratings of therapeutic alliance at weeks 4 and 10, ratings of

quality of care and amount helped by treatment at week 10, and ratings of goal satisfaction, plans to continue using treatment, and likelihood to recommend treatment to others at week 12.

Sample Size and Power: We propose to screen 4,789 potential participants, anticipating we will enroll 1,250 participants to arrive at a final sample of 1,000 evaluated participants, assuming a 20% dropout rate by the last assessment. In our previous psychotherapy studies, dropout rates have been on the order of 10% by final assessment. In our recent on-line studies with Google Verily, drop out has been on the order of 20%. Our large incentive arm, tested in Phase 1, is based on the incentive analyses done on the Baseline Mood Study at Verily.

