Statistical Analyses: See Table 2 for analyses by hypothesis. Treatment disengagement, treatment response, and remission will be analyzed using chi-square tests and Cramér V effect sizes. 2-level linear mixed effects models using full information maximum likelihood (FIML) and an unstructured covariance matrix with client nested within clinician will be used for analyses at a single timepoint. Models predicting binary outcomes at a single timepoint will be evaluated using 2-level logistic regression models with Cholesky factorization with client nested within clinician, with Level 2 condition as the independent variable. Effect sizes for these models will be computed via pooled standard deviations of conditions at that timepoint.

Models assessing changes across time will be evaluated using 3-level mixed effects regression models with timepoint nested within client nested within clinician using FIML and an unstructured covariance matrix. Client-level effects will be allowed to randomly vary, and clinician will be a clustering variable with condition approximately balanced within clinicians. Analyses with time from baseline to week 12 will include a spline variable to account for differences in outcome trajectories from baseline to week 5 and from week 6 to week 12.

The mixed-effects models will utilize all available data. Prior research has demonstrated equivalence of longitudinal mixed model analyses using imputed versus non-imputed data (e.g., between multiple imputation and FIML).¹³ Theoretically, there is no reason to expect substantial differences between FIML and MI with a reasonable sample size and complete predictors.¹⁴ Thus, missing data will not be imputed. Cohen's *d* clinical outcome effect sizes for the model predicting PHQ-9 scores by Level 2 condition from weeks 6 to 12 will be computed as the difference between model-estimated means divided by the pooled standard deviations when the second condition

was assigned at week 6. All remaining clinical outcome effect sizes will be computed as the difference between model-estimated means divided by the pooled baseline standard deviations.

We will use the Benjamini-Hochberg procedure to account for Type 1 error by adjusting for familywise error within hypothesis families (e.g., within Hypotheses 1a to 1d; within Hypothesis 2). *P* values and effect sizes with 95% confidence intervals will be reported, as appropriate.¹⁵

Table 2. Analyses by Hypothesis

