Hypothesis	Timepoint(s)	Statistical Test	Contrast/analysis of interest
1a: Compared to those randomized to weekly video care at baseline, patients randomized to message-based care will have greater improvements in depression	Baseline to W5	3-level mixed effects model	MBP vs VBP
1b: Compared to those randomized to weekly video care at baseline, patients randomized to message-based care will have greater improvements in social functioning	Baseline to W12	3-level mixed effects model	MBP vs VBP
1c: Compared to those randomized to weekly video care at baseline, patients randomized to message-based care will be more likely to show a treatment response at 5 and 12 weeks of care.	Between W3 to W5 / W12	Chi-square tests	MBP vs VBP
1d: Compared to those randomized to weekly video care at baseline, patients randomized to message-based care will be more likely to experience remission at 5 and 12 weeks of care.	Between W3 to W5 / W12	Chi-square tests	MBP vs VBP
2: For those who fail to respond to treatment from baseline to 5 weeks, those re-randomized to receive (or retain) weekly video care will have greater improvements in depression than those randomized to monthly video care	W6 to W12	3-level mixed effects model with time centered at week 6	MBP+VBP _{weekly} vs MBP+VBP _{monthly} ; VBP _{weekly} +MBP vs VBP _{monthly} +MBP
2: For those who fail to respond to treatment from baseline to 5 weeks, those re-randomized to receive (or retain) weekly video care will be more likely to show a response to treatment than those randomized to monthly video care	W12	Chi-square test	MBP+VBP _{weekly} vs MBP+VBP _{monthly} ; VBP _{weekly} +MBP vs VBP _{monthly} +MBP
3 (moderator): Baseline anxiety will moderate improvement in depression such that those with greater anxiety will have better response to message-based care at 5 and 12 weeks than to video-based care.	Baseline to W12	3-level mixed effects model, with mean-centered baseline GAD-7	MBP vs VBP

Exploratory: We will explore whether there will be differences among groups in treatment engagement by week 5	Between W3 to W5	Chi-square test	MBP vs VBP
Exploratory: We will explore whether there will be differences among groups in ratings of therapeutic alliance	W4 / W10	2-level mixed effects models	W4: Level 1 conditions (MBP vs VBP); W10: Level 2 conditions (MBP vs VBP; MBP+VBP _{monthly} vs MBP+VBP _{weekly} ; VBP _{monthly} +MBP vs VBP _{monthly} +MBP)

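### Free improvement: test remission (Hypothesis 1d) with baseline PHQ-9 and clinician in the model instead of an unadjusted chi-square test

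*Combined protocol and SAP*

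**What the plan says.** Hypothesis 1d in section 8.0 is that "patients randomized to message-based care will be more likely to experience remission at 5 and 12 weeks of care". The Statistical Analyses text assigns the method: "Treatment disengagement, treatment response, and remission will be analyzed using chi-square tests and Cramér V effect sizes". Row 1d of Table 2 agrees: chi-square tests of MBP versus VBP, with the first outcome taken between weeks 3 and 5 and the second at week 12. The p values enter the Benjamini-Hochberg adjustment over Hypotheses 1a to 1d.

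Section 8.0 also describes two-level logistic models for binary outcomes at a single timepoint. They are written "with Level 2 condition as the independent variable", name no covariate, and appear in Table 2 only for exploratory week-12 ratings.

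The covariate exists. Section 4.3 states: "Phase 2 participants will provide information needed to assess eligibility including date of birth, location, PHQ-9, phone number, email address, and primary language prior to" being enrolled, and adds: "This information is retained as part of study data". The PHQ-9 is also on the baseline list in section 5.2. Entry normally requires a score of at least 10, but section 4.4 allows that, after a wait for a therapist, "participants with PHQ-9 scores between 5 and 10 may be randomized if they remain interested in participating in the study". Section 5.1 blocks Level 1 randomisation by therapist and not by severity.

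**The concern.** Within Hypothesis 1, only remission makes no use of the starting score. The longitudinal models for 1a and 1b include baseline as a timepoint, and response (1c) is defined relative to baseline. If remission is a low absolute score, people who start lower are more likely to reach it, so baseline PHQ-9 is likely prognostic. Leaving a prognostic covariate out of a binary comparison gives up power. It also leaves the realised estimate exposed to whatever severity difference chance produces.

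Two features of the plan point to the same change. Under Accounting for Provider Effects, section 8.0 says that the primary analyses will all be clustered on provider, by mixed models or generalised estimating equations; a chi-square test cannot do this. And Cramér V for a two-by-two table has no sign, whereas 1d is directional and section 8.0 plans effect sizes with 95% confidence intervals.

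**Working it through.** **Inputs from the plan.** Section 8.0 plans to "enroll 1,250 participants to arrive at a final sample of 1,000 evaluated participants", with 20% dropout, a 0.20 SD difference in PHQ-9, and a binary example of 60% versus 70% for response.

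**Assumptions.** Allocation is 1:1 (500 per arm) and tests are two-sided at 5%. The text available for review gives no remission cut-off, remission rate, baseline-to-follow-up correlation or power for remission, so these are varied below.

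**1. The plan's own figures.**
- Enrolment: 1,000 / (1 − 0.20) = 1,250. Reproduced.
- 0.20 SD: 0.20 / √(2/500) − 1.96 = 3.162 − 1.96 = 1.202, so power is 88.5%.
- 60% versus 70%: [0.10 − 1.96 × √(2 × 0.65 × 0.35 / 500)] / √[(0.24 + 0.21) / 500] = (0.10 − 0.0591) / 0.0300 = 1.36, so power is 91.3%.

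Both powers agree with the stated figure of more than 80%. Neither concerns remission.

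**2. Chi-square power for remission at the planned effect.** Assume remission means PHQ-9 below 5, follow-up SD 5 and follow-up mean 9.0 or 7.5. A 0.20 SD shift then gives roughly 18% versus 24%, or 28% versus 35%. By the formula in step 1:
- 18% versus 24%: (0.06 − 0.0505) / 0.0257 = 0.37, so power is about 64%.
- 28% versus 35%: (0.07 − 0.0576) / 0.0293 = 0.42, so power is about 66%.

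Simulated chi-square power was about 58% to 69%, in line with this.

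**3. Gain from adjustment at the planned effect.** Unadjusted chi-square was compared with single-level logistic regression on arm and baseline PHQ-9 (baseline scores 10 to 27, 500 per arm, 1,500 to 3,000 simulated trials per setting). The gain in power was:
- correlation 0 to 0.2: about 0 to 1 point
- 0.3: about 2 points
- 0.5: about 5 to 7 points (for example 62.0% to 66.8%, and 69.2% to 75.4%)
- 0.6: about 8 to 11 points

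At 1,500 trials, the Monte Carlo standard error is about 1.2 points per power figure.

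**4. Same comparison from an effect giving about 80% chi-square power** (2,500 trials per setting). R² is the share of variance in the remission indicator explained by baseline.

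| Correlation | 30.0% v 38.3%: R² | chi-square → adjusted | 20.0% v 27.45%: R² | chi-square → adjusted |
|---|---|---|---|---|
| 0 | 0.000 | 79.7% → 79.6% | 0.000 | 79.6% → 79.2% |
| 0.2 | 0.022 | 79.0% → 79.2% | 0.019 | 79.5% → 79.9% |
| 0.3 | 0.049 | 78.7% → 81.3% | 0.039 | 78.8% → 81.0% |
| 0.4 | 0.085 | 80.0% → 83.8% | 0.068 | 78.6% → 82.3% |
| 0.5 | 0.130 | 78.0% → 84.4% | 0.104 | 79.6% → 85.2% |
| 0.6 | 0.187 | 79.0% → 87.5% | 0.144 | 80.4% → 87.9% |

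As equivalent sample size, 1,000 / (1 − R²) is 1,053 at R² = 0.05, 1,111 at 0.10 and 1,250 at 0.20.

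**5. Chance imbalance.** The SE of the baseline mean difference is √(2/500) = 0.063 SD, so its 95% range is ±1.96 × 0.063 = ±0.124 SD. An imbalance at that edge moves the unadjusted remission difference by about 1.0 to 1.3 percentage points at correlation 0.3 and 2.0 to 2.5 points at 0.6. Over all randomisations the mean error was at most 0.2 points, which is consistent with no bias.

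**The case against.** The strongest reply is that nothing here is wrong. A chi-square test of a randomised contrast is valid, and its error rate already allows for chance imbalance. The named primary outcome is the quantitative PHQ-9, whose model does use baseline. The plan claims no power for remission, so no stated figure fails. The gain depends on an unstated correlation, and the entry floor of 10 narrows the baseline range, which tends to lower that correlation. All of this stands, and it is why the point is a free improvement and not an error.

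A reader might infer three stronger things that the documents do not support:
- **That baseline imbalance biases the 1d comparison.** It does not on average; it only adds to the variability of the single realised estimate.
- **That a 0.1 SD imbalance, at correlation 0.5, shifts the result by 0.05 SD, a quarter of the planned effect.** That arithmetic is for a continuous PHQ-9 contrast. Remission is binary, and the shifts in step 5 are the relevant ones.
- **That the starting score determines who can remit.** With no cut-off or correlation in the text, the most that can be said is that it is likely prognostic.

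Two limits also stand. The simulations had no clinician effect, so they are for single-level logistic regression and not the exact model proposed, and they left out participants entering below 10. The clustering statement covers primary analyses, and the plan does not say whether 1d is one. The chi-square test is therefore in tension with that statement, not in plain contradiction of it.

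**Conclusion.** The point holds as a free improvement. The planned test of remission is valid, but it leaves aside a covariate held for every Phase 2 participant and takes no account of provider. The cost is negligible if baseline and follow-up PHQ-9 are correlated at 0.2 or less, about 2 points of power at 0.3, and about 5 to 11 points at 0.5 to 0.6. These figures assume 500 per arm, a 0.20 SD difference, remission as PHQ-9 below 5 and the remission rates in step 2. Under those assumptions the chi-square test has only about 58% to 69% power for remission, so the recoverable power is useful. The baseline argument is confined to 1d: for response (1c), already scaled to baseline, adjustment changes power by only about 0 to 3 points.

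**What to change.** In section 8.0 (Statistical Analyses) and row 1d of Table 2:
- Make the test of remission the two-level logistic model the SAP already describes (client within clinician), with Level 1 condition (MBP versus VBP) and continuous baseline PHQ-9 as predictors.
- Report the model-standardised risk difference with 95% CI at week 5 and at week 12 in place of Cramér V. An adjusted odds ratio is a different quantity from the unadjusted one, and standardising avoids that difficulty.
- Enter this model's p value in the Hypothesis 1 Benjamini-Hochberg family.
- Keep the raw percentages and the chi-square test as supportive results.
- State the remission cut-off beside the model if it is not defined elsewhere.

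The cost is a sentence or two in the SAP, one table cell and a few lines of code; no new data are needed. The change should be made before outcome data by arm are seen, because a covariate chosen afterwards would carry little weight.

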Level 1 Power: For the quantitative primary outcome (PHQ-9) we have greater than 80% power to detect a 0.20 standard deviation across groups which corresponds to a clinically meaningful small difference. For a binary success indicator, we will consider a 50% reduction in PHQ-9 from baseline to week 5, and we have greater than 80% power to detect an absolute difference of 10% (e.g., 60% of subjects with >50% improvement versus 70% of subjects with >50% improvement).

Level 2 Power: The primary comparison in the second stage is the comparison of the Ultimate Plan (UP; MBP with weekly VBP) versus the Premium Plan (PP; MBP with monthly VBP) for each of the first stage randomization groups (MBP and VBP). We expect a second stage analysis sample of 324 subjects, and this corresponds to 80% power to detect a 0.32 standard deviation difference across the UP and PP groups when pooling across the primary MBP and VBP strata. Our primary second stage analysis will construct an overall UP versus PP difference stratifying on first stage randomization, and secondary analysis will consider the UP versus PP difference within the MBP and VBP groups separately.

Accounting for Provider Effects: Each provider will treat both MBP and VBP patients. Therefore, our primary analyses will all cluster on provider either using linear mixed models or generalized estimating equations to yield valid statistical inference. However, since treatment condition will vary within provider, the impact of provider clustering is to effectively balance or control for provider effects. Therefore, our power calculations are conservative since they do not account for the potential increase in precision associated with control for provider effects. Such within-provider randomization is in contrast to traditional cluster randomized trials where providers treat all patients in one study condition and thus increase variability associated with treatment comparisons through the well-known intra-cluster correlation coefficient.

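### The plan says Benjamini-Hochberg adjusts for familywise error; it controls the false discovery rate, and within Hypothesis 1 familywise error can modestly exceed 5%

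*Combined protocol and SAP*

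**What the plan says.** The multiplicity rule is one sentence under Statistical Analyses in section 8.0: "We will use the Benjamini-Hochberg procedure to account for Type 1 error by adjusting for familywise error within hypothesis families". The families are given by example only: "e.g., within Hypotheses 1a to 1d; within Hypothesis 2". Neither a significance level nor a false discovery rate q is stated. The nearest indication is that "effect sizes with 95% confidence intervals will be reported", which points to 5%. The term false discovery rate does not appear in the document, and nothing elsewhere corrects the sentence.

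The number of tests per family is also left open.

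- **Hypothesis 1.** The hypothesis statement ends with "be more likely to experience remission (1d) at 5 and 12 weeks of care", and the two timepoints can be read as applying to all of 1a to 1d, which gives eight tests. Table 2 gives one model each for 1a and 1b, and two timepoints each for 1c ("will be more likely to show a treatment response at 5 and 12 weeks of care") and 1d, which gives six. Counting the four labelled hypotheses gives four.
- **Hypothesis 2.** The Level 2 power paragraph makes a pooled contrast primary and adds that "secondary analysis will consider the UP versus PP difference within the MBP and VBP groups separately". Table 2 lists only the within-stratum contrasts, for two outcomes.

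**The concern.** The sentence attaches to a procedure an error rate that the procedure does not control in general. Familywise error is the chance of at least one false rejection in the family. The false discovery rate is the expected share of rejections that are false. The second can be held at 5% while the first is higher.

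The difference matters when results are mixed. Hypothesis 1 makes separate claims on depression, social functioning, response and remission. If some of these effects are real and others are not, a report that familywise error was controlled across them would be incorrect, and a reader would take each claim as more secure than the method makes it.

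**Working it through.** **Inputs.** The final sample of 1,000 evaluated participants and the 0.20 SD effect come from the sample size and Level 1 power paragraphs ("we have greater than 80% power to detect a 0.20 standard deviation across groups"). The Level 2 figures are "We expect a second stage analysis sample of 324 subjects, and this corresponds to 80% power to detect a 0.32 standard deviation difference". Assumptions: equal allocation (500 per arm), two-sided tests, level 0.05.

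**The plan's own power figures.** With unadjusted two-sided 0.05 they reproduce:

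- Level 1, 0.20 SD: noncentrality 0.20 × √(500/2) = 3.162; power = Φ(3.162 − 1.960) = 88.5%, against a stated figure above 80%.
- Level 1, 60% versus 70%: 91%, against a stated figure above 80%.
- Level 2, 0.32 SD pooled: noncentrality 0.32 × √(324/4) = 2.88; power = Φ(2.88 − 1.960) = 82%, against a stated 80%.

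The plan states no familywise error figure, so there is none to reproduce.

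**Where familywise error is held.** If every null is true, any rejection is a false discovery, so the two error rates coincide and both are at most 5% under the dependence condition (simulated maximum 0.0501). If only one null remains, it can be rejected only when its p-value is at most 0.05, so its error is at most 5% under any dependence. A family of two tests always falls under one of these cases or has no true null.

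**Where it is not held.** Take four independent tests with two real effects that are certain to be rejected. The remaining nulls face cut-offs of 0.05 × 3/4 = 0.0375 for the smaller p-value and 0.05 for the larger. Familywise error = 1 − (1 − 0.0375)² + (0.05 − 0.0375)² = 0.0736 + 0.0002 = 7.4%.

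**Hypothesis 1 at the planned effect.** Simulation of equicorrelated two-sided z-tests (400,000 replicates, key settings repeated with 1,000,000), half the effects real with noncentrality 3.162:

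| Tests in family | Correlation 0.5 | Correlation 0.7 | Holm, same settings |
|---|---|---|---|
| 4 | 5.7% | 4.8% | 3.8%, 3.3% |
| 6 | 6.8% | 5.3-5.4% (between runs) | 3.5%, 3.0% |
| 8 | 7.8% | 5.8% | 3.4%, 2.8% |

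Independent tests would give 6.7%, 8.6% and 10.4%. The simulated false discovery rate with half the effects real, including the independent case, is 2.3-2.6%, in line with (half the tests null) × 0.05 = 2.5%.

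**Hypothesis 1 with near-certain real effects.** The worst case at correlation 0.5 is 6.9% for four tests, 8.7% for six and 10.2% for eight.

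**Hypothesis 2 at 0.32 SD, 324 subjects.** Two pooled tests with one effect real: 4.0-4.5%. Four stratum tests (assumed equal strata of 162, noncentrality 0.32 × √(162/4) = 2.036): 5.0-5.3% with one real and 4.2-4.8% with two real.

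**The case against.** The strongest reply is that this is a slip of wording. No test, p-value or sample size changes if the procedure is kept, the plan states no numerical familywise level, and Benjamini-Hochberg does hold familywise error when every null is true. That stands, and it is why the point is minor. It does not remove the point, because the sentence names an error rate and the method lacks that property in exactly the mixed case that Hypothesis 1 invites.

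A second reply is that the excess is small in this trial. Depression and response rest on the PHQ-9, and remission presumably does too (the documents do not define it), so the tests are positively correlated. A simulation of the six Table 2 tests treated response and remission as cuts of a score shifted by 0.20 SD (assumed event rates 50% and 30%, noncentralities about 2.5 and 2.4) with assumed correlations of 0.4-0.6 between weeks and between depression and functioning. Familywise error ran from 3.4% to 6.5% over five patterns of real effects, an excess of 0 to 1.5 points. This also stands, but only at the planned effect: larger real effects raise the figure, so neither this range nor the table above is a general bound.

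A reader might infer more than the documents support:

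- **That familywise error reaches 8.6% or 10.4%.** Those figures need independent tests, which does not fit outcomes that mostly share one scale.
- **That the procedure is unsuitable.** It controls the false discovery rate, and nothing in the plan requires strict familywise control beyond this one phrase.
- **That the power figures are wrong.** They reproduce at an unadjusted two-sided 5% level, and the plan does not say that they are adjusted.
- **That the choice is between six and eight tests, or two and four.** Four labelled hypotheses is also a fair reading for Hypothesis 1, and the spline could give 1b more than one contrast. Hypothesis 2 could hold six tests if pooled and stratum contrasts both count.

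**Conclusion.** The sentence is wrong as written: it credits Benjamini-Hochberg with familywise control, and the procedure controls the false discovery rate. The consequence is modest and confined to families in which at least one effect is real and two or more nulls remain. At the planned effect, with half the Hypothesis 1 effects real and correlation 0.5-0.7, familywise error lies between about 4.8% (four tests) and 7.8% (eight tests); with much stronger effects it reaches about 7-10% at correlation 0.5. For Hypothesis 2 at its design effect the excess is at most 0.3 points with four stratum tests, and there is none with two pooled tests. These sizes depend on the assumed level, allocation, correlation and pattern of real effects; the mismatch between procedure and error rate does not. Severity: minor.

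**What to change.** Keep Benjamini-Hochberg. Replace the phrase about adjusting for familywise error with: *by controlling the false discovery rate at q = 0.05 within each family (valid under independence or positive dependence of the tests)*. The value 0.05 is an inference from the confidence level, so the authors should confirm it. Make no familywise-error claim in the report. This costs one phrase and no power.

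With the same edit, list the tests that belong to each family. Any of the counts above is workable, but it should be fixed before the data are seen because it sets the cut-offs: for the smallest p-value, 0.05/4 = 0.0125, 0.05/6 = 0.0083 or 0.05/8 = 0.0063. This is a request for detail and does not carry the point.

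Only if familywise control is really intended should the plan name Holm instead. The price is power: with six tests, three of them real at 0.20 SD, power per real effect falls from about 79-81% to 73%. The power section needs no change.
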